2. ANALYSIS PLAN

2.1. Primary analysis

2.1.1 Definition of analysis populations

The primary analysis will be based on the per-protocol (PP) analysis for the primary endpoint. The companion intent-to-treat (ITT) analysis will also be completed and reasons for disagreement will be evaluated. A “positive” trial is one in which the primary hypothesis is true for both the PP and ITT analyses.

- ITT: All randomized patients (i.e., excluding those in the parallel cohorts), analyzed according to randomization assignment.
- PP: All randomized patients (i.e., excluding those in the parallel cohorts) who satisfy all of the following conditions:
 - Completed follow-up through at least the 6 month visit (note that per-protocol, the 6 month visit and subsequent long-term follow-up visits may be conducted via phone).
 - Received 80-120% of doses of anticoagulant medication based on protocol-prescribed randomized duration of anticoagulation.
 - Had no protocol violations in eligibility criteria.

- c) Safety: All randomized patients who have received at least 1 dose of anticoagulant post-enrollment.

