^c Repeat testing of any APA testing that was positive at diagnosis or if not done at screening.

^d Telephone questionnaire available in the Manual of Operations (MOO)

^a The original protocol contained telephone visits for visits 5 and 6; current visit schedule has not been renumbered, so as to avoid inconsistency in visit numbering/tracking relative to prior protocol versions.

^{**}The 6 month, 1 year, and 2 year visit may be conducted as a telephone visit if the site has been unsuccessful in getting the participant to return for an in-person follow-up visit (in which case the PTS assessment is not performed).

[#]Eligibility for enrollment must be confirmed by CCC prior to enrollment. Eligibility for randomization must be confirmed by CCC prior to randomization or assigning to parallel cohort. See MOO for additional details.

[%]PTS Assessment required if visit done in person.

[^] Manco-Johnson Instrument; for participating sites (if applicable), may include Modified Villalta Scale in addition to Manco-Johnson Instrument

For all participants, additional pertinent clinical data will be captured as follows: nature of the initial venous thrombosis episode (with detail as to signs/symptoms, symptom onset, anatomic site, and veno-occlusion); results of coagulation and thrombophilia testing; antithrombotic agents employed (both acute and sub-acute) and their intensities (i.e., results of standard anticoagulant monitoring assays); lag time from symptom onset to achievement of therapeutic anticoagulant levels; veno-occlusion and thrombus resolution at 6 weeks; nature of any major or minor bleeding episodes (as defined in Section IV B, above) during the anticoagulant therapy period (with detail as to amount of any related blood transfusion and/or any anticoagulant reversal required—see also Data and Safety Monitoring Plan section); and nature of any recurrent VTE (with detail as to signs/symptoms, anatomic site, and veno-occlusion). Data collection case report forms (CRFs) and SAE report forms derived directly from the web-based electronic data capture system are provided in the MOO. All adverse events and anticoagulant adherence in a calendar (example supplied in the MOO) from time of enrollment through the end of the sub-acute anticoagulant treatment.

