A patient who develops a DVT while pregnant who has no other provoking factor beyond the pregnancy will remain ineligible for this study.

F. Description and Justification of Procedures, Measures, and Data Collection Tools:

Except as noted above (i.e., at some participating centers in which thrombophilia testing employed in participant qualification for enrollment is not routinely performed as part of best/standard clinical care), the only laboratory assays, examinations, or other procedures performed solely for the purposes of this study and not currently part of best/standard clinical care are the additional 10 mL blood specimens (6 mL for infants) obtained at 6 weeks and 3 months for protocol-specified prognostic marker investigations and future unspecified research (i.e., biobanking, when permission given for the latter via opt-in during the informed consent process). These biospecimens will be stored in the Johns Hopkins All Children's Pediatric Biorepository at the Clinical Coordinating Center. All biospecimen storage tubes are pre-labeled with a unique 2D barcode, with the association between the barcode and the participant's unique study ID maintained in the Biorepository's secure, web-based, password-protected Lab Information Management System (LIMS) maintained behind the information technology firewall at Johns Hopkins All Children's Hospital. Biospecimens will be used to identify and validate putative prognostic biomarkers in pediatric venous thrombosis (predictors/modifiers of risk of outcomes – recurrent VTE, bleeding, PTS). The genetic investigations will involve candidate gene, a genome-wide association study (GWAS), and whole genome sequencing approaches in deoxyribonucleic acid, as well as confirmatory approaches in the transcriptome (mRNA). In addition, we will perform non-genetic "omics" investigations involving proteomics/peptidomics, metabolomics, and lipidomics (Goldenberg et al., 2014). The Johns Hopkins All Children's Pediatric Biorepository uses a secure database to store all data related to the samples, behind the institutional firewall. Following completion of the protocol-specified aims, external requests for specimens in the Kids-DOTT trial biobank will be vetted and made available through the National Institutes of Health (NIH), in accordance with NIH policies on data and biospecimen sharing. Throughout their study participation, up to and including visit 4, patients will be asked to record adverse events and medication adherence in a diary (See MOO).

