The statistical analysis plan was developed by [name], biostatistician expert on the trial's Steering Committee, and Lead Biostatistician at the DCC. The primary hypothesis concerns non-inferiority of shortened-duration when compared with conventional duration anticoagulation therapy. In accordance with the convention for non-inferiority trials, the primary analysis is per-protocol (PP) for the primary endpoint. Analytic populations will be defined as follows:

- a) Intent-to-treat (ITT): All randomized patients (i.e., excluding those in the parallel cohorts), analyzed according to randomization assignment.
- b) Per-protocol: All randomized patients (i.e., excluding those in the parallel cohorts) who: completed follow-up through at least the 6 month visit; received 80% and 120% of doses of anticoagulant medication based on protocol-prescribed randomized duration of anticoagulation; AND had no protocol violations in eligibility criteria.
- c) Safety: All randomized patients who have received at least 1 dose of anticoagulant post-enrollment.

The original design of the Kids-DOTT trial was based on historical observational studies which report a 10% annual rate of recurrent VTE and a 10% annual rate of clinically relevant bleeding. In the first half of the trial the risk has been much lower than the original design assumptions; that is, the observed risk is about 3% for recurrent VTE and about 1% for the bleeding endpoint. The updated Kids-DOTT statistical analysis plan describes how the bivariate decision curve will be revised when the recurrent VTE and bleeding risks differ from the pre-trial estimates. The analysis plan does not include an interim analysis because the reduced risk for the VTE and bleeding endpoints does not provide sufficient information to support an interim analysis prior to trial completion.

[figure not shown]

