2.1.3 Analysis methods for primary endpoints

The primary efficacy analysis will estimate/test the ARR for clinically relevant bleeding and symptomatic VTE recurrence. The ARR and 95% confidence intervals will be estimated using the exact methods of Fay et al.[3] using the R package exact2x2. Non-inferiority will be decided if the 95% confidence rectangle rules out the non-inferiority curve defined by Appendix equation (2). Note that the exact confidence intervals of Fay et al. will result in a discrete decision curve instead of the smooth curve illustrated by the lines in Figure 2. The primary analysis will use data from the PP population, but the ITT analysis will also be conducted and reported as confirmatory.

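### The primary per-protocol population has no exception for endpoint events or death, so some events can remove their own participant from the primary estimate

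*SAP*

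**What the plan says.** Protocol IV.H states that "the primary analysis is per-protocol (PP) for the primary endpoint", and SAP 2.1.1 and 2.1.3 agree. Both documents give three PP conditions:

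- Follow-up: "Completed follow-up through at least the 6 month visit" (a telephone visit is enough, per SAP 2.1.1).
- Doses: "Received 80-120% of doses of anticoagulant medication based on protocol-prescribed randomized duration of anticoagulation" in the SAP, and "received 80% and 120% of doses of anticoagulant medication based on protocol-prescribed randomized duration of anticoagulation" in Protocol IV.H.
- No eligibility violation.

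The first two are judged after randomization. Neither mentions a primary endpoint event or death. Protocol IV.J.1 classes recurrent VTE, bleeding and death as outcome events but gives them no rule for PP membership. The only stated protection from PP disqualification, the starred deviations in Protocol IV.J.2, is administrative.

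Three passages of the Protocol bear on the dose rule without settling it. Section IV.F says that "up to and including visit 4, patients will be asked to record adverse events and medication adherence in a diary". The text after Table 2 in IV.D describes the adverse-event and adherence calendar as running "from time of enrollment through the end of the sub-acute anticoagulant treatment". The end of IV.D says that children with outcome visits stay in the primary analysis of recurrent VTE and post-thrombotic syndrome. It does not define those visits, does not mention bleeding, and is not carried into either PP definition.

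On success, SAP 2.1.1 says that a positive "trial is one in which the primary hypothesis is true for both the PP and ITT analyses". SAP 2.1.3 says only that "the ITT analysis will also be conducted and reported as confirmatory". Protocol IV.H defines the ITT population but states no joint rule.

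**The concern.** A population used for the primary estimate should not depend on whether the outcome occurred. Here an endpoint event can itself cause the failed condition: a bleed can end treatment, a death ends follow-up, and a recurrence can restart treatment. The participant and the event then leave the primary analysis together.

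The routes are not symmetric between arms. The shortened course is complete at 42 days, so a later bleed in that arm cannot push adherence below 80%, whereas one in the conventional arm can. With so few events expected, a single exclusion matters to the reported PP difference and can matter to the PP decision.

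**Working it through.** **Inputs.** PP size 316, or 158 per arm (Protocol IV.H, SAP 1.3.2). Risks of 3% for symptomatic recurrent VTE (srVTE) and 1% for bleeding (SAP introduction). Shortened course of at least 42 days (Protocol IV.F, Visit 2). The decision rule is that the 95% limits must rule out equation (2) (SAP 2.1.3 and Appendix). Three months is taken as 84 to 90 days, an assumption.

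**The plan's own figures.** 420 × 0.75 = 315, against 316 stated. The half-widths 1.96 × √(p(1−p) × 4/316) are 0.038 for p = 0.03 and 0.022 for p = 0.01, matching SAP Table 4.

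**Dose limits in days.**
- Conventional arm, lower limit: 0.8 × 84 = 67.2 and 0.8 × 90 = 72.
- Shortened arm, upper limit: 1.2 × 42 = 50.4, so more than 8.4 further days exceed it if they count.
- Conventional arm, upper limit: 1.2 × 84 = 100.8 and 1.2 × 90 = 108. About 17 to 18 days of re-treatment would exceed it, again only if those doses count.

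**Expected events per arm.** srVTE 0.03 × 158 = 4.7; bleeds 0.01 × 158 = 1.6.

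**Effect of one removal.** Solving equation (2) for srVTE, with S_arr = √(0.1 × 0.9 × 2/285) = 0.02513 and U_B the upper limit for bleeding:

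bound = 0.025 + 1.96 S_arr − 0.003/(0.08 + 1.96 S_arr − U_B) = 0.07426 − 0.003/(0.12926 − U_B).

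Upper limits are melded exact 95% limits, the method the SAP cites, coded numerically. Counts are shortened v conventional, with bleeds 1 v 1.

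| srVTE | upper limit, srVTE | U_B | bound | PP result |
|---|---|---|---|---|
| 5/158 v 5/158 | 4.75% | 3.02% | 4.40% | fails |
| 4/157 v 5/158 | 3.94% | 3.04% | 4.39% | passes |

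Using S_arr = 0.0251 as printed lowers each bound by less than 0.01 point and changes neither result.

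A removed conventional-arm bleed acts the other way. Going from bleeds 1 v 1 to 1 v 0 raises U_B from 3.02% to 3.48% and lowers the bound from 4.40% to 4.25%.

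**If recurrence treatment counts, with doses taken to visit 4.** A shortened-arm recurrence would have to occur early enough for 8.4 days of re-treatment before day 84. The share removed is (84 − 8.4 − 42)/322 = 10.4%, where 322 days is week 6 to week 52. This assumes a constant hazard and that every recurrence is re-treated. With visit 4 at day 74 or 94 the share is 7.3% or 13.5%.

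At the bound with no bleeding difference, the srVTE difference is 0.07426 − 0.003/0.12926 = 5.1 points (8.1% v 3%). After a 10.4% removal, the shortened-arm risk is 0.081 × 0.896/(1 − 0.081 × 0.104) = 7.3%, so PP shows 4.3 points. The chance that PP alone declares non-inferiority rises from 0.7% to 1.6%.

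**Bleeds dropped from the conventional arm (shares assumed).** Dropping 30% or 60% lowers the PP pass probability from 54% to 52% or 51% (bleeding 0.3% v 1.7%, no srVTE difference), and from 45% to 43% or 42% (1% v 1%).

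**The case against.** The strongest answer is that the trial decision is already protected. A positive trial needs PP and ITT together, ITT contains every randomized patient, and SAP 2.1.1 promises to evaluate reasons for disagreement. The joint error cannot exceed that of ITT alone, which exclusions from PP do not touch. This stands, provided ITT keeps all events. Even PP alone, at 1.6%, stays below a one-sided 2.5%.

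Second, the dose rule refers to the assigned duration, so it can fairly be read as adherence to the assigned course. Treatment of a new recurrence would then not count. This also stands as a reading, so the recurrence route is conditional. It does not remove the other two routes: a conventional-arm bleed that stops treatment early still falls below 80%, and an early death still fails the 6-month rule.

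Third, the bleeding route is small, and nothing in the documents says how often a bleed ends treatment. That is correct, and the 30% and 60% shares are illustrations.

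A reader might infer that these exclusions make PP and ITT disagree far more often. The plan's sizes do not support that. With ITT at about 210 per arm (420/2), full ITT outcomes, no true difference and a 10.4% share, trials passing on PP alone rise only from about 2.3% to 4.5%, and total disagreement does not increase. A reader might also take missing source documents for an outcome (Protocol IV.J.2) as a further PP exclusion. It is not among the three PP conditions.

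**Conclusion.** The gap is real on the wording of both documents and deserves correction, but its reach is limited. Applied as written, the PP rules remove a conventional-arm bleed that permanently stops treatment before about day 67 to 72, and any fatal event before month 6. They remove re-treated shortened-arm recurrences only on a reading that Protocol IV.D and IV.F leave open.

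One removal can change the PP decision (5 v 5 fails, 4/157 v 5/158 passes). How often removals would occur is unknown, and the documents give no death rate from which to size the follow-up route.

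It would be tempting to conclude that the PP definition is tilted toward non-inferiority or that the trial could falsely succeed because of it. Neither follows. Losing shortened-arm recurrences favours non-inferiority, losing conventional-arm bleeds works against it, and ITT must also succeed. What remains is a primary PP estimate open to outcome-dependent exclusion, and possibly a power loss of about 1 to 3 points under the assumed shares.

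**What to change.** In SAP 2.1.1 and Protocol IV.H:

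1. For a participant with an adjudicated primary endpoint event or death, compute the 80 to 120% ratio only up to the date of the first such event. The cost is that these participants are judged over a shorter period than the rest.
2. Do not treat death, or an adjudicated event before month 6, as failing the follow-up condition. Event-free early losses stay excluded, so PP risks rise slightly. If a fraction L is lost before month 6, with on average 10 of 46 weeks at risk (0.03 × 10/46 = 0.0065), the 3.0% risk becomes ((1 − L) × 0.03 + L × 0.0065)/((1 − L) + L × 0.0065). That is 3.1% for L = 12.5% and 3.2% for L = 25%, both assumed. Report beside it a sensitivity analysis that drops the 6-month condition for everyone.
3. Reconcile the calendar and retention statements in Protocol IV.D and the diary statement in IV.F with the dose rule. State the PP-and-ITT success rule in the same words in SAP 2.1.1, SAP 2.1.3 and Protocol IV.H.

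The cost is wording plus one sensitivity analysis. No new data are needed and the planned 316 is unchanged. Protocol IV.I reports that the primary database was locked in March 2021. If PP membership was fixed then, report the corrected PP set as a sensitivity analysis.

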2.1.2 Definition of endpoints

Primary efficacy and safety endpoints are defined as:

Efficacy: Occurrence of symptomatic recurrent VTE within 1 year.

Safety: Occurrence of clinically-relevant (major plus clinically-relevant non-major) bleeding within 1 year.

Treatment effects will be measured by the ARR for the efficacy and safety events over the 12-months interval using the centrally adjudicated events.

2.1.3 Analysis methods for primary endpoints

The primary efficacy analysis will estimate/test the ARR for clinically relevant bleeding and symptomatic VTE recurrence. The ARR and 95% confidence intervals will be estimated using the exact methods of Fay et al.[3] using the R package exact2x2. Non-inferiority will be decided if the 95% confidence rectangle rules out the non-inferiority curve defined by Appendix equation (2). Note that the exact confidence intervals of Fay et al. will result in a discrete decision curve instead of the smooth curve illustrated by the lines in Figure 2. The primary analysis will use data from the PP population, but the ITT analysis will also be conducted and reported as confirmatory.

2.2. Secondary analyses

2.2.1 Secondary endpoints

The secondary efficacy endpoints include:

- 1) Occurrence of symptomatic recurrent VTE or development of post-thrombotic syndrome (PTS) (composite endpoint) within 1 year;
- 2) Occurrence of symptomatic recurrent VTE within 2 years;
- 3) Development of PTS within 1 year;
- 4) Development of PTS within 2 years.

Post-thrombotic syndrome can only occur in subjects in which the index VTE occurred in a lower or upper extremity or inferior/superior vena cava; the secondary efficacy analyses that involve PTS (including the composite secondary efficacy endpoint) will therefore be restricted to those subjects. The definition of PTS will be based upon the presence of objective signs of chronic venous insufficiency, using the CEAP component of the Manco-Johnson Instrument, as described in the recommendations for endpoint definitions for pediatric VTE trials from the International Society on Thrombosis and Haemostasis [4].

2.2.2 Analysis methods for secondary endpoints

The main secondary efficacy analysis will compare the risk of the composite of symptomatic recurrent VTE or PTS within 12-months of the index VTE event in subjects with a lower or upper extremity (including vena cava) index deep vein thrombosis event (referred to as the “PTS/VTE” composite). As in the primary analysis the risks within each treatment group will be estimated using the exact methods of Fay et al.[3] as implemented in the R package exact 2x2.

Risk difference (ARR) for the secondary efficacy endpoint will be calculated in both the ITT and PP analysis populations (defined in Section 2.1.1). The risk difference for the secondary safety endpoint will also be calculated in the safety population. The risk difference for the secondary efficacy endpoints will be calculated across all stratification variables (i.e., age group, thrombus location group), and separately within each level of the stratification variables. The differences between groups and 95% confidence intervals will be reported separately for each comparison. Non-inferiority will be judged by the estimated ARR and 95% confidence interval; there will be no formal bivariate decision curve for the secondary endpoint analysis.

2.2.3 Missing data

The PTS component of the PTS/recurrent VTE composite endpoint is evaluated at the 12-month visit and participants who do not complete the 12-month visit will be missing the PTS component of the composite endpoint. The analysis of section 2.2.2 will be performed using data only from subjects who have completed the 12-month visit and have both PTS and recurrent VTE assessment without imputation for missing data.

2.3 Analysis of tertiary and exploratory endpoints

2.3.1 Analysis of subgroups

If there are a sufficient number of events, the ARR for the primary and secondary efficacy and safety endpoints will be calculated separately within each level of the stratification variables.

3. APPENDIX: Bivariate decision criteria

The bivariate decision curve for the design of Kids-DOTT was derived from the 3 reference points in **Table 1** that were selected to capture a clinically meaningful balance between the potential benefits of symptomatic recurrent VTE risk reduction and the potential for increased clinically relevant bleeding risk. The bivariate decision curve of **Figure 1** is given by equation (1) below, which is based on the standard error of the ARR (S_{arr}) assuming a 10% risk for recurrent VTE and a 10% risk for clinically relevant bleeding. The bivariate NI bound is given by equation (2), which is the curve that is shifted by 1.96 standard errors to the northeast of the decision curve. If the bleeding and VTE risks differ from the original assumptions, then the revised decision curve shifted by 1.96 standard errors to the southwest of the NI bound (equation 3). The shifted decision curve (**Figure 2**, green line) is given by equation (3) using a 3% risk of symptomatic recurrent VTE ($\pi_V = 0.03$) and a 1% risk of clinically relevant bleeding ($\pi_B = 0.01$).

$$\text{ARR decision curve: } (ARR_V - 0.025)(ARR_B - 0.08) = 0.003 \quad (1)$$

$$\text{ARR null curve: } (ARR_V - 0.025 - 1.96S_{arr})(ARR_B - 0.08 - 1.96S_{arr}) = 0.003 \quad (2)$$

$$\text{Shifted decision curve: } (ARR_V - 0.025 - 1.96S_{arr} + 1.96S_{arr}^V)(ARR_B - 0.08 - 1.96S_{arr} + 1.96S_{arr}^B) = 0.003 \quad (3)$$

where $S_{arr} = \sqrt{0.1 \times 0.9 \times 2/285} = 0.0251$, $S_{arr}^V = \sqrt{\pi_V \times (1 - \pi_V) \times 2/285}$, and $S_{arr}^B = \sqrt{\pi_B \times (1 - \pi_B) \times 2/285}$, where π_V and π_B denote the 1-year risk of recurrent VTE and clinically relevant bleeding, respectively.

REFERENCES

